5.6 Clinical Laboratory Evaluations

Blood samples and urine specimens for laboratory evaluation will be collected at screening per Schedule of Study Procedures ([Appendix A](#)).

Urine samples will be collected at screening for amphetamines, barbiturates, benzodiazepine metabolites, cocaine metabolites, methadone, opiate metabolites, phencyclidine, marijuana metabolites, and cotinine. For alcohol, saliva test will be utilized.

The presence of HIV antibody, HbSAg, and Hepatitis C antibody will be assessed at screening.

5.6.1 Hematology

Complete blood cell count (CBC) will include a standard red blood cell (RBC), hemoglobin, hematocrit, white blood cell (WBC) with differential, and platelet count.

5.6.2 Serum Chemistry

Comprehensive metabolic panel will include serum alkaline phosphatase, alanine aminotransferase (ALT), aspartate aminotransferase (AST), glucose, calcium, phosphorus, chloride, sodium, potassium, blood urea nitrogen (BUN), creatinine, total bilirubin, albumin, total protein, amylase, bicarbonate/carbon dioxide (CO₂), uric acid, and lactate dehydrogenase (LDH).

5.6.3 Coagulation

Coagulation will include PT and aPTT.

5.6.4 Urinalysis

Urinalysis will include pH, specific gravity, glucose, protein, ketones, blood and a detailed microscopic analysis. Microscopic analysis will be performed and will include the following: WBC, RBC and bacteria.

5.6.5 Pregnancy Test

A urine pregnancy test will be administered to females of childbearing potential at screening.

6.0 EFFICACY

Efficacy assessments will be evaluated based on self-reported and clinical assessments of pruritus at pre-dose, and at 5 (\pm 2 min), 10 (\pm 2 min), 15 (\pm 3 min), 30 (\pm 5 min), 45 (\pm 5 min), 60 (\pm 10 min), 120 (\pm 10 min) minutes, and every 60 minutes (\pm 10 min) after dosing until the discharge criteria (the time when symptoms of acute urticaria have been effectively treated based on the Investigator's or his/her designee's opinion will be recorded, not necessarily when

subjects discharged) is met for acute flare and until urticaria symptoms returns to the baseline for chronic spontaneous urticaria. If the time to return to baseline for chronic spontaneous urticaria is beyond 4 hours, such time may be recorded by the patient and reported in the follow-up call. The actual time of the assessment and of when the symptoms return to the baseline will be recorded. Subjects should also report the date and time of recurrence, if any, of symptoms after they leave the clinic.

The following efficacy assessments will be evaluated:

- A patient reported pruritus/hive score from 0 (none) to 3 (severe) for itch and hive using UAS twice daily as below:

| Itch Severity Score | Amount of Itch | Itch Severity at Each Assessment |
|---------------------|----------------|--|
| 0 | None | None |
| 1 | Mild | Minimal awareness, easily tolerated |
| 2 | Moderate | Definite awareness, bothersome but tolerable |
| 3 | Intense | Difficult to tolerate |

| Hive Severity Score | Number of Hives at Each Assessment |
|---------------------|------------------------------------|
| 0 | None |
| 1 | 1-6 |
| 2 | 7-12 |
| 3 | >12 |

- Patient reported pain associated with the urticaria flare will be recorded based on a self-reported VAS score,
- An investigator-rated extent of urticaria; % of body area with urticaria (Grade 1: urticarial lesions covering < 10% BSA; Grade 2: urticarial lesions covering 10-30% BSA; Grade 3: urticarial lesions covering > 30% BSA),
- An investigator-rated erythema score (0 = none, 1 = almost clear [slight redness], 2 = mild erythema [definite redness], 3 = moderate erythema [marked redness], 4 = severe erythema [fiery redness]).

[REDACTED]

[REDACTED]

7.0 PHARMACOKINETICS

No PK measures will be assessed during this study.

8.0 PHARMACODYNAMICS

No PD measures will be assessed during this study.

9.0 SAFETY ASSESSMENTS

9.1 Collection of Adverse Events Data

Data regarding TEAEs will be collected in this study. TEAEs are events that are not present at baseline, or if present at baseline, have worsened in severity. AEs will be assessed while the subjects are in the study. AEs assessed by the Investigator as related to study drug and “ongoing” at discharge will be monitored by the Investigator until resolved or until the subject is deemed “lost to follow-up”.

Any AEs reported by the subject or noted by the Investigator or his/her designee will be recorded on the eCRF regardless of the Investigator opinion of causality. The following information will be recorded for each AE: description of the event, date and time of onset, date and time of resolution, severity, causal relationship to study drug, outcome, action taken with the study drug and any treatment given.

All abnormal changes from baseline will be collected, graded with regards to severity or clinical significance, assessed for causal relationship and recorded on the eCRF.

Refer to [Section 13.0](#) for further details.

9.2 Complete or Targeted Physical Examination

The Investigator will perform a complete PE at screening. A targeted PE will be performed pre-dose in each Treatment Period. Results will be recorded on the appropriate page of the eCRF.

9.3 Vital Signs

Vital signs (BP, PR, respiratory rate, and temperature) will be assessed at screening and at pre-dose and at 5 (\pm 2 min), 20 (\pm 2 min), 30 (\pm 2 min), 60 (\pm 5 min), and 120 (\pm 5 min) minutes after dosing in each Treatment Period.

Actual reading time at the measurement by hour/minutes/seconds will be recorded for each assessment.

The Investigator will assess vital signs on an ongoing basis and make sure the BP is within normal limit before study drug dosing.

10.0 STUDY VISITS AND PROCEDURES

Refer to [Appendix A](#) for the Schedule of Study Procedures.

10.1 Screening (Days -90 to -1)

The Investigator or his/her approved designee must explain the nature of the study protocol and associated risks to the potential study participant. The potential participant must be allowed to review the study information and to ask questions before being asked to sign the Informed Consent Form (ICF). Written informed consent must be provided by the potential study participant prior to initiation of any screening evaluations or other study-related procedures. The signature date and the name of the individual at the site who obtained the informed consent will be recorded in the subject's medical record.

After written informed consent is obtained, the subject will be assigned a screening number and will undergo the designated screening procedures listed in Appendix A. The Investigator, Sub-Investigator or delegate will assess the results of these screening evaluations to determine eligibility for entry into the study according to the inclusion/exclusion criteria listed in [Section 4.0](#).

Screening evaluations may be performed up to 90 days in advance of dosing but must be completed at least one (1) day prior to Day 0.

The following study evaluations and procedures are required to determine eligibility:

- Obtain and record a medical history, including demographics, prior medications, and concomitant medications.
- Complete PE
- Vital signs
- Height and weight measurements
- Blood and serum samples for the following laboratory evaluations:
 - Hematology
 - Serum chemistry
 - Coagulation
 - HIV antibody
 - Hepatitis screening
- Urinalysis, urine drug, alcohol and cotinine screen (Saliva test for alcohol may be utilized)
- Urine pregnancy test

- 12-lead ECG (performed in triplicate)

10.2 Pre-dose Evaluations (Treatment Periods 1 - 3)

Subjects will return to the site when experiencing an acute flare of urticaria symptoms or chronic spontaneous urticaria before taking other acute medications. Urticaria symptoms and severity will be assessed based on both patient-reported and clinician-based assessments. Pre-dose assessments include the following:

- Admission to clinical site
- Confirm eligibility (Treatment period 1 only)
- Confirm medical history (Treatment period 1 only)
- Targeted PE
- Concomitant medications
- Vital signs
- Patient-reported pruritus/hive score and VAS for pain
- Investigator-rated extent of urticaria and erythema score

10.3 Drug Administration

After baseline safety assessments, subjects will be randomized to receive the following treatments at each of the three Treatment Periods:

- 1 mg per 100 μ L dose of ARS-1,
- 2 mg per 100 μ L dose of ARS-1, or
- placebo (100 μ L)

ARS-1 or placebo will be dosed to the nostril by the medical professional in a clinical setting per IFU ([Appendix B](#)). [REDACTED]

[REDACTED] Subjects will be monitored for both safety and symptom relief. Safety assessments will be performed after dosing and will include AEs and vital signs. Concomitant medications will be recorded.

Subjects should remain in the clinic as below:

- Acute flare: at least 2 hours after dosing and can discharge when the discharge criteria is met (the time when symptoms of acute urticaria have been effectively treated based on the investigator's or his/her designee's opinion will be recorded, not necessarily when subjects discharged). If no relief of pruritus symptoms after 2 hours, other acute interventions may be administered as rescue.

- Chronic spontaneous urticaria: until the urticaria symptoms returns to the baseline. [REDACTED]

The calendar date and 24-hour clock time of all doses will be recorded on the eCRF.

10.4 Post-dose Evaluations (Treatment Periods 1 - 3)

Post-dose assessments include the following:

- Vital signs
- Concomitant medication
- AEs
- Patient reported pruritus/hive score and VAS for pain
- Investigator-rated extent of urticaria and erythema score

- [REDACTED]

- [REDACTED]

- [REDACTED]

10.5 Discharge Assessments (Treatment Periods 1 - 3)

Discharge assessments will be completed by the Investigator or his/her designee once symptoms of urticaria have been effectively treated for an acute flare or returned to baseline for chronic spontaneous urticaria. Actual time by hours and minutes will be recorded. In addition, AEs and concomitant medication will also be recorded.

11.0 PREMATURE DISCONTINUATION FROM STUDY

A premature discontinuation from study will occur when a subject who signed informed consent ceases participation in this study, regardless of circumstances, prior to completion of the protocol. Subjects can be prematurely discontinued from the study for one of the following reasons:

- Failure to meet inclusion/exclusion criteria before receiving first dose of study drug has been administered
- Death
- Significant safety event that in the opinion of the Investigator warrants discontinuation

- Lost to follow-up after every attempt has been made to contact the subject, including sending a registered letter
- Subject withdraws consent

The Principal Investigator and the IRB/EC reserve the right to prematurely terminate the study in the interest of subject safety and welfare. The Sponsor reserves the right to prematurely terminate the study at any time for administrative reasons.

12.0 PRODUCT SPECIFICATIONS

12.1 Description

Epinephrine, illustrated in [Figure 1](#), is a sympathomimetic catecholamine. Chemically, epinephrine is B-(3, 4dihydroxyphenyl)-a-methyl-aminoethanol. Epinephrine solution deteriorates rapidly on exposure to air or light, turning pink from oxidation to adrenochrome and brown from the formation of melanin. In addition to oxidation, epinephrine is also susceptible to racemization at very low pH and photolysis.

ARS-1 is a solution formulation of epinephrine intended for nasal administration. [REDACTED]

12.2 Formulation, Packaging, and Labeling

[REDACTED] single label panel
containing the following information:

ARS-1 (Intranasal Epinephrine)
Single-Use Spray
1.0 mg (100 µL at 10 mg/mL)
Lot Number: XXXXXXXX
Manufacturing Date: MMMYYYYY
Storage Conditions: Protect from light – store in package until ready to use

OR

ARS-1 (Intranasal Epinephrine)
Single-Use Spray
2.0 mg (100 µL at 20 mg/mL)

Lot Number: XXXXXXXX

Manufacturing Date: MMMYYYYY

Storage Conditions: Protect from light – store in package until ready to use

[REDACTED]

[REDACTED]

[REDACTED]

[REDACTED]

[REDACTED]

[REDACTED]

[REDACTED]

full Good Manufacturing Practice (GMP) conditions.

12.6 Accountability of Study Drugs

All study drugs received, dispensed, and returned must be accounted for in the study drug Dispensing Log, including:

- Subject number and initials
- Date study drug was dispensed
- Quantity dispensed
- Quantity returned
- Quantity wasted, as applicable

All study drug received and dispensed by the Investigator will be inventoried and accounted for throughout the study. The study drug must be stored in a restricted area with limited access. Contents of the study drug containers must not be combined. Used sprayers will be accounted for and disposed appropriately.

The Investigator must maintain an accurate, up to date Dispensing Log for all study drugs supplied by the Sponsor. Study drug dispensed for all subjects must be recorded on the Drug Accountability Form. The study drug Dispensing Log and remaining drug inventory will be reviewed at each monitoring visit by the Sponsor-designated clinical monitor.

The study drug supplied for this study is for use only in subjects properly consented and enrolled into this protocol. Study drugs must be kept in a secure location physically separated from standard clinic or office drug supplies.

13.0 SAFETY MONITORING AND ADVERSE EVENTS

13.1 Adverse Events

Data regarding TEAEs will be collected in this study. TEAEs are events that are not present at baseline, or if present at baseline, have worsened in severity.

Definition of Adverse Events and Adverse Drug Reactions:

AEs in the eCRF will be classified according to the most recent FDA definitions and in a manner consistent with International Conference on Harmonization (ICH) guidelines. As such the following definitions will be used:

An AE is any unfavorable and unintended sign, symptom, or disease temporally associated with the use of an investigational (medicinal) product (IP) or other protocol-imposed intervention, regardless of attribution. An AE may include intercurrent illnesses or injuries that represent an exacerbation (increase in frequency, severity, or specificity) of pre-existing conditions (e.g., worsening of asthma). A laboratory abnormality will be reported on the “Adverse Event” case report forms only if it is associated with clinical sequelae or requires therapeutic intervention.

Whenever possible, it is preferable to record a diagnosis as the AE term rather than a series of symptoms relating to a diagnosis. AEs will be coded according to the Medical Dictionary for Regulatory Activities (MedDRA) and graded according to the Common Terminology Criteria for Adverse Events (CTCAE) v 5.0 ([Appendix C](#)).

The reporting period for AEs starts after dosing and continues until discharge.

If an AE remains unresolved at discharge, the subject will be followed, at the Investigator’s discretion, until resolution of the event or until the subject is deemed “lost to follow-up”. AEs assessed by the Investigator as related to study drug and “ongoing” at discharge will be monitored by the Investigator until resolved or until the subject is deemed “lost to follow-up”. SAEs must be followed until resolution by the PI, even if this extends beyond the study-reporting

period. Resolution is defined as the return to baseline status or stabilization of the condition with the expectation that it will remain chronic.

The Investigator will assess AEs for severity, relationship to IP, and as to whether the event meets one or more of the definitions of an SAE. The assessments will be recorded on the source documents and AE case report form (CRF), using the categories defined below.

| Causality Category | Description |
|---------------------------|--|
| Unlikely | A clinical event, including laboratory test abnormality, with a temporal relationship to drug administration which makes a causal relationship improbable, and in which other drugs, chemicals or underlying disease provide plausible explanations. For the purpose of this protocol, the term unlikely will be considered not related to study medication and an “Adverse Event”. |
| Possible | A clinical event, including laboratory test abnormality, with a reasonable time sequence to administration of the drug, but which could also be explained by concurrent disease or other drugs or chemicals. Information on drug withdrawal may be lacking or unclear. For the purpose of this protocol, an event that has possible relationship to study medication will be defined as a “Suspected Adverse Drug Reaction”. |
| Probable | A clinical event, including laboratory test abnormality, with a reasonable time sequence to administration of the drug, unlikely to be attributed to concurrent disease or other drugs or chemicals, and which follows a clinically reasonable response on withdrawal. For the purpose of this protocol, an event that has probable relationship to study medication will be defined as an “Adverse Drug Reaction”. |

In order to classify AEs and diseases, preferred terms will be assigned by the Sponsor or its designee to the original terms entered on the eCRF, using MedDRA.

For those AEs that are not described on the CTCAE v 5.0 ([Appendix C](#)), such AEs will be graded on a 5-point scale (mild, moderate, severe, life-threatening, death) and reported as indicated on the CRF. Intensity of such an AE is defined as follows:

Table 8: Severity Assessment Terminology for Reporting Adverse Events

| Grade | Common Term | Description |
|-------|------------------|--|
| 1 | Mild | Mild; asymptomatic or mild symptoms; clinical or diagnostic observations only; intervention not indicated. |
| 2 | Moderate | Moderate; minimal, local or noninvasive intervention indicated; limiting age-appropriate instrumental Assisted Daily Living (ADL). |
| 3 | Severe | Severe or medically significant but not immediately life-threatening; hospitalization or prolongation of hospitalization indicated; disabling; limiting self-care ADL. |
| 4 | Life-Threatening | Life-threatening consequences: urgent intervention indicated. |
| 5 | Death | Death related to AE |

13.2 Serious Adverse Events

According to the ICH Guidelines for Good Clinical Practice (E6), an SAE is any untoward medical occurrence during the course of a clinical investigation that is characterized by one or more of the following:

- Results in death
- Is life-threatening
- Requires in-subject hospitalization or prolongation of existing hospitalization
- Results in persistent or significant disability/incapacity
- Is a congenital anomaly/birth defect
- Important medical events

Hospitalization admissions scheduled prior to the study are not considered SAEs unless the hospitalization is prolonged due to an AE. However, such hospitalization should be documented in the Investigator's comment in the eCRF. Hospitalizations for scheduled treatments of a

preexisting condition that has not worsened or hospitalization for fewer than 24 hours does not meet the category of “New or prolonged hospitalization”.

13.3 Pregnancy Reporting

Although not an SAE, exposure to study drug during pregnancy, even if no AE is reported in the mother, should be reported within 24 hours.

13.3.1 Reporting Requirements for Serious Adverse Events

All SAEs must be reported to the Sponsor by the Investigator, study coordinator, other designated study personnel, or clinical research associate within 24 hours of notification of the SAE. To report such events, an SAE form must be completed by the Investigator and sent within 24 hours by email or fax with relevant information.

Within the 48 hours following the initial report, the Investigator must provide further information on the SAE if available. This should include a copy of the completed SAE form, and any other information that will assist the understanding of the event. Significant new information on ongoing SAEs should be provided promptly as a follow-up.

The Investigator also must report all SAEs promptly to the appropriate IRB/EC as required by the institution within 24 hours or 48 hours if on weekend/holiday.

Table 9: Contact Information for SAE Reporting

| | |
|------------|------------|
| [REDACTED] | [REDACTED] |
| [REDACTED] | [REDACTED] |
| [REDACTED] | [REDACTED] |
| [REDACTED] | [REDACTED] |
| [REDACTED] | [REDACTED] |
| [REDACTED] | [REDACTED] |
| [REDACTED] | [REDACTED] |
| [REDACTED] | [REDACTED] |

13.3.2 Recording of Serious Adverse Events

All SAE information must be recorded on the SAE form provided by the Sponsor. Additional follow-up information (e.g., test results, autopsy, and discharge summary) must be obtained to supplement the SAE report form. A copy of all initial and follow-up reports must be filed with the subject’s eCRF.

14.0 STATISTICAL CONSIDERATIONS

14.1 Sample Size Determination

The sample size is based on practical consideration. [REDACTED]

14.2 Analysis Data Sets

| Data Analysis Set | Definition | Analysis |
|------------------------------------|--|------------------------|
| Intent-To-Treat (ITT) analysis set | Any subjects who are randomized and received at least one treatment. Subjects will be analyzed per randomization scheme. | Demographics |
| Modified ITT (mITT) analysis set | A subset of the ITT analysis set that includes subjects who received treatment and have post-treatment efficacy data from at least two treatments. | Efficacy [REDACTED] |
| Safety analysis set | Subjects who are randomized and received at least one treatment. Subjects will be analyzed based on the treatment received at each treatment period. | Safety |

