| Statistical Analysis | 
All quantitative endpoints will be analyses using linear mixed models with fixed effects for treatment and period and a random effect for subject. For each endpoint, the following comparisons will be made using two-sided tests at the $\alpha=0.05$ level of significance:
 
 1 mg ARS-1 vs Placebo 2 mg ARS-1 vs Placebo 
There will be no adjustments for multiplicity; hence, all analyses will be viewed as exploratory and hypothesis generating, rather than confirmatory.
 |
| Study Duration | 
It is anticipated that each subject will participate in the study for up to 120 days, which comprises a 90-day screening period and 3-4-week study period during which three acute flares of urticaria symptoms will be treated.
 |
| Study Centers | 
Up to Four (4) Centers
 |

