3.0 STUDY DESIGN

3.1 Description of Study Design

This is a Phase 2, single-dose, randomized, placebo-controlled, crossover study that will consist of a screening period and an open-label treatment period. Subjects enrolled will have acute urticaria with known etiology or have chronic spontaneous urticaria with unknown etiology at least two (2) times a week while on a chronic treatment.

Each subject will be randomized to receive either a single treatment of ARS-1 (1 mg and 2 mg dose) or placebo nasal spray and then will be crossed over to receive other treatments during an acute urticaria flare. Efficacy will be primarily assessed using a patient reported pruritus/hive score and VAS for pain. Clinical assessments will also be conducted by the Investigator after dosing ARS-1.

██████████ eligible male or female subjects, 18 to 65 years of age, with urticaria who experience acute flares while on a chronic treatment regimen or chronic spontaneous urticaria with unknown etiology at least two (2) times a week will be randomized to receive ARS-1 (1 mg dose), ARS-1 (2 mg dose), or placebo. After screening subjects will return to the clinical site when experiencing an acute flare of urticaria symptoms or chronic spontaneous urticaria.

Screening Period: Subjects will be screened to assess eligibility for the clinical trial. All subjects will undergo safety screening evaluations within 90 days prior to treatment.

Open-Label Treatment Period: Subjects will return to the site when experiencing an acute flare of urticaria symptoms or chronic spontaneous urticaria before taking other acute medications. Urticaria symptoms and severity will be assessed based on both patient-reported and clinician-based assessments. After baseline safety assessments, subjects will be randomized to receive the following treatments at each of the three Treatment Periods:

- 1 mg per 100 µL dose of ARS-1,
- 2 mg per 100 µL dose of ARS-1, or
- placebo (100 µL)

If possible, rescue medication should be avoided for 15 minutes after dosing. Subjects will be monitored for both safety and symptom relief. Safety assessments will be performed after dosing and will include AEs and vital signs. Concomitant medications will be recorded.

Subjects should remain in the clinic as below:

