3.1.1 Randomization/Assignment to Study Drug

subjects with urticaria who experience acute flares while on a chronic treatment regimen or chronic spontaneous urticaria with unknown etiology at least two (2) times a week will be enrolled and randomized to receive the following treatments in each Treatment Period:

- 1 mg/100 μ L dose of ARS-1,
- 2 mg/100 μ L dose of ARS-1,
- placebo

To ensure proper wash-out between the IN doses, each subject will be randomized to one of the following sequences:

- 1 mg ARS-1 IN: placebo: 2 mg ARS-1 IN
- 2 mg ARS-1 IN: placebo: 1 mg ARS-1 IN

The side (right or left) of dosing will be alternated per randomization.

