14.3 Efficacy Data Analyses

14.3.1 Primary Efficacy Analyses

The baseline for the primary endpoints will be the pre-dose at each visit.

Superiority comparison of ARS-1 1 mg vs. placebo and ARS-1 2 mg vs. placebo at each timepoint will be tested at the two-sided 0.05 significance level. If both ARS-1 1 and 2 mg are statistically superior to placebo, comparison between the ARS-1 doses will be conducted.

Time to effect is defined to be the time that it takes to lower one grade, two grades, and three grades.

Duration of effect is defined as the time from when the grade becomes above baseline until the grade returned to baseline.

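### The only visible efficacy set drops everyone who stops after Period 1; almost all the data lost are ARS-1 data, and the resulting bias has unknown sign

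*Combined protocol and SAP*

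**What the plan says.** Section 14.2 defines three analysis sets. The ITT set is "Any subjects who are randomized and received at least one treatment. Subjects will be analyzed per randomization scheme", and the use listed for it is demographics. Efficacy goes to the modified ITT (mITT) set: "A subset of the ITT analysis set that includes subjects who received treatment and have post-treatment efficacy data from at least two treatments". The rest of that efficacy cell is redacted, as is section 14.5. The visible text has no efficacy analysis on a wider set and no rule for missing periods.

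Section 3.1.1 lists two sequences, "1 mg ARS-1 IN: placebo: 2 mg ARS-1 IN" and "2 mg ARS-1 IN: placebo: 1 mg ARS-1 IN". The general design text in the Synopsis and section 3.1 is looser. There a subject "will be randomized to receive either a single treatment of ARS-1 (1 mg and 2 mg dose) or placebo nasal spray" and then crosses over, which can be read as allowing placebo first.

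The Synopsis (Statistical Analysis) specifies "linear mixed models with fixed effects for treatment and period and a random effect for subject". Section 14.3.1 adds the test: "Superiority comparison of ARS-1 1 mg vs. placebo and ARS-1 2 mg vs. placebo at each timepoint will be tested at the two-sided 0.05 significance". The Synopsis also says that nothing is adjusted for multiplicity and that all results are exploratory.

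**The concern.** Whether a subject enters the efficacy set is settled after randomisation, and after that subject has seen what the first spray did. Under section 10.2 a subject has to come back to the site in a new flare, before taking other acute medication. Section 11.0 lists safety events, withdrawn consent and loss to follow-up among the ways out. Any of these may be connected with the Period 1 experience.

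In many crossover trials such a rule would remove active and placebo data in similar amounts. Here it cannot. With ARS-1 always first and placebo always second, a subject who leaves after one period takes ARS-1 data out of the analysis, while one who leaves after two normally stays in. If leaving is related to response, the ARS-1 means shift and the placebo mean has no matching loss. A small difference from placebo, in either direction, could then reflect selection rather than the drug.

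**Working it through.** The plan gives no power, SD or dropout figure to reproduce; section 14.1 bases the sample size on practical grounds.

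**Who is removed under the section 3.1.1 sequences**

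| Last period with efficacy data | Treatments with data | In mITT? |
|---|---|---|
| Period 1 | one ARS-1 dose | no |
| Period 2 | one ARS-1 dose, placebo | yes |
| Period 3 | all three | yes |

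The set counts efficacy data, not sprays. A subject with no Period 1 scores who leaves after placebo would also be removed. This should be rare, so the data lost are almost all, but not strictly all, ARS-1 data.

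**Size of the bias**

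From the plan: N = 32 and the two sequences. Assumed, because the plan gives no values: no true effect; within-subject SD σw = 0.8; between-subject SD σb = 0.4 or 0.8; subjects in the worst quarter of Period 1 response leave with probability 0.5 or 0.8; everyone else completes three periods. The excluded fraction is q = 0.25 × 0.5 = 12.5% or 0.25 × 0.8 = 20%.

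With positive values meaning improvement, pooled ARS-1 minus placebo in a completer is (Y1 + Y3)/2 − Y2. The subject effect cancels, which leaves half of the Period 1 error averaged over those who stay:

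bias = ½ × (σw²/σ) × k × q/(1 − q), where σ = √(σw² + σb²) and k = φ(z₀.₂₅)/0.25 = 0.318/0.25 = 1.271.

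| σb | q | σ | Calculation | Bias |
|---|---|---|---|---|
| 0.4 | 12.5% | 0.894 | ½ × 0.716 × 1.271 × 0.143 | +0.065 |
| 0.4 | 20% | 0.894 | ½ × 0.716 × 1.271 × 0.250 | +0.114 |
| 0.8 | 12.5% | 1.131 | ½ × 0.566 × 1.271 × 0.143 | +0.051 |
| 0.8 | 20% | 1.131 | ½ × 0.566 × 1.271 × 0.250 | +0.090 |

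If the best quarter leaves instead, symmetry reverses every sign. If leaving is random, the bias is 0. Simulation of the same settings agrees with all three patterns. A random-subject model on all treated subjects gave about 0 in every case.

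The sampling SD of the contrast among completers is σw × √(1.5/n). This is 0.8 × √(1.5/28) = 0.185 at 12.5% excluded and 0.8 × √(1.5/25.6) = 0.194 at 20%, so about 0.19. The bias is then 0.05/0.19 = 0.26 to 0.11/0.19 = 0.58 of a sampling SD.

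**Wider range**

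A second simulation used SD units, within-subject correlation 0.3 to 0.7 and 10% to 30% leaving after Period 1, again with no true effect.

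| Leaving | Bias, worst leave | Bias, best leave | Rejection at two-sided 5%, worst leave |
|---|---|---|---|
| 10% | +0.03 to +0.06 | −0.02 to −0.06 | 4% to 6% |
| 20% | +0.04 to +0.10 | −0.04 to −0.11 | 6% to 9% |
| 30% | +0.07 to +0.16 | −0.07 to −0.15 | 7% to 12% |

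Random leaving gave −0.004 to +0.013. With all treated subjects, the bias was −0.008 to +0.013 and rejection 4.3% to 5.7% throughout.

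**Why the period term was left out**

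Under section 3.1.1 each ARS-1 dose falls in Period 1 or 3 and placebo always falls in Period 2. The two dose indicators therefore sum to the Period 1 and Period 3 indicators in every row. The stated treatment-plus-period model has five columns and rank four. Each dose versus placebo is not estimable, although 1 mg versus 2 mg is. This holds for either analysis set.

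**The case against.** A reader might infer that the rule discards only ARS-1 failures and so biases the trial in one direction, in favour of ARS-1. The documents do not support that. The rule removes Period 1-only subjects whatever their reason: a good responder with no further flare, a safety withdrawal, an unrelated loss. Lack of efficacy is not a listed reason for discontinuation in section 11.0. A subject without relief may be rescued under section 10.3, and if that subject returns, the data stay in. Poor responders failing to return is plausible, but nothing in the plan shows it.

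The case for leaving the rule alone has four further parts.

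- Eligibility requires symptoms at least twice a week, so further flares should be common and exclusions may be few. This limits the size but does not remove the selection.
- The analyses are declared exploratory. This lowers the consequence. Section 14.3.1 still plans superiority tests at 0.05 and makes the between-dose comparison depend on them.
- A further analysis set or sensitivity analysis may lie behind the redactions. That is possible, and it limits confidence.
- The planned model cannot estimate the placebo contrasts on any set, so the near-zero bias with all treated subjects belongs to a model without period. This is correct, and it is a larger, separate flaw. It does not justify the exclusion.

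**Conclusion.** The point holds with moderate confidence. The visible efficacy set selects on a post-randomisation event and, under the listed sequences, removes almost only ARS-1 data. The size is modest and the sign unknown: about 0.05 to 0.11 points either way at 12% to 20% excluded, against a sampling SD of about 0.19, and about 0 if leaving is unrelated to response.

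These sizes rest on assumed SDs, assumed dropout and a model with no period term. The near-zero result with all treated subjects also assumes that leaving, where it is not random, depends on the recorded Period 1 response. If it depended on something unrecorded, the wider set would not be guaranteed free of bias. The claim does not extend to a demonstrated bias in favour of ARS-1.

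**What to change.** In section 14.2, define the main efficacy set as all randomised subjects who received at least one treatment and have any post-dose efficacy score, analysed as randomised. Keep the two-treatment set as a sensitivity analysis. Report the number excluded from it by sequence and by reason. This changes one table row, adds one summary table and needs no new data.

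Two related matters need separate action. The change of set does not make ARS-1 versus placebo estimable alongside period while placebo is always second, so the sequences and the stated model have to be made compatible. The Synopsis and section 3.1 wording on the first treatment must also be reconciled with section 3.1.1. If placebo could come first, the loss would no longer fall almost wholly on ARS-1 data, but the set would still select on a post-randomisation event.
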